Appendix 1. Definition of Organ Failure and Sepsis

The definition of organ failure encompasses three organ systems, respiratory system, renal system and cardiovascular system.

For the respiratory system, organ failure will be defined as:

- PaO₂/FiO₂ ≤300 determined by arterial blood gas or imputed using pulse oximetry, or
- The use of high flow nasal cannula, non-invasive or invasive mechanical ventilation

For the renal system, in patients without known chronic kidney disease (baseline eGFR ≥60 mL/min/1.73 m²), organ failure will be defined as:

- An increase in serum creatinine ≥300% if the baseline creatinine is known from prior to the hospitalization for AP, or
- A serum creatinine ≥ 1.9 mg/dL, or
- The initiation of renal replacement therapy

For patients with pre-existing chronic kidney disease (baseline GFR <60 mL/min/1.73 m²), organ failure will be defined as:

- An increase in serum creatinine ≥300% if the baseline creatinine is known from prior to the hospitalization for AP, or
- An increase of serum creatinine to a level >4.0 mg/dl, or
- The initiation of renal replacement therapy

For the cardiovascular system, organ failure will be defined as:

- A systolic blood pressure <90 mmHg that is not fluid responsive, or
- The use of either vasopressor or inotropic support

Sepsis is the life-threatening organ dysfunction caused by a dysregulated host response to infection. For this study, organ dysfunction in the setting of infection will be defined by the presence of one of the following criteria:

- PaO₂/FiO₂ ≤300 determined by arterial blood gas or imputed using pulse oximetry
- The use of noninvasive or invasive mechanical ventilation
- Platelet count <100 x10³/uL
- Total bilirubin ≥2.0 mg/dL
- The use of vasopressor or inotropic support
- Serum creatinine ≥1.9 mg/dL in patients without pre-existing chronic kidney disease

- Serum creatinine >4.0 mg/dL in patients with pre-existing chronic kidney disease
- An increase in serum creatinine ≥300% if the baseline creatinine is known from prior to the hospitalization for acute pancreatitis
- The initiation of renal replacement therapy

Modified Marshall Scoring System: Organ Dysfunction in Acute Pancreatitis

		0 (None)	1 (None)	2 (Mild)	3 (Moderate)	4 (Severe)
Respiratory	PaO ₂ /FiO ₂	>400	301-400	201-300	101-200	≤100
Renal	Serum Cr mg/dL	<1.4	1.4-1.8	1.9-3.6	3.7-4.9	>4.9

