CV no inotrope	SBP mmHg	≥90	<90 fluid responsive	<90 not fluid responsive	<90, pH <7.3	<90, pH <7.2

CV = cardiovascular Adapted from Banks 2013

Appendix 2. American Gastroenterological Association Institute Guideline on the Initial Management of Acute Pancreatitis

	Recommendation	Strength	Quality
1a.	In patients with AP, the AGA suggests using goal-directed therapy for fluid management. Comment: The AGA makes no recommendation whether normal saline or Ringer's lactate is used.	Conditional	Very Low
1b.	In patients with AP, the AGA suggests against the use of HES fluids	Conditional	Very Low
2	In patients with predicted severe AP and necrotizing AP, the AGA suggests against the use of prophylactic antibiotics	Conditional	Low
3	In patients with acute biliary pancreatitis and no cholangitis, the AGA suggests against the routine use of urgent ERCP	Conditional	Low
4	In patients with AP, the AGA recommends early (within 24 h) oral feeding as tolerated, rather than keeping the patient nil per os	Strong	Moderate
5	In patients with AP and inability to feed orally, the AGA recommends enteral rather than parenteral nutrition	Strong	Moderate
6	In patients with predicted severe or necrotizing pancreatitis requiring enteral tube feeding, the AGA suggests either NG or NJ route	Conditional	Low
7	In patients with acute biliary pancreatitis, the AGA recommends cholecystectomy during the initial admission rather than after discharge	Strong	Moderate
8	In patients with acute alcoholic pancreatitis, the AGA recommends brief alcohol intervention during admission	Strong	Moderate

AGA = American Gastroenterological Association; AP = acute pancreatitis; ERCP = endoscopic retrograde cholangiopancreatography; HES = hydroxyethyl starches; NG = nasogastric; NJ = nasojejunal

Adapted from Crockett 2018

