8.7.8 Incidence, Severity, and Duration of Organ Failure

The incidence, severity and duration of organ failure will be defined by the development of severe respiratory failure or severe renal failure or severe cardiac failure. Severe respiratory failure will be defined as those patients receiving invasive mechanical ventilation (IMV) or those receiving for ≥ 48 hours use of either high flow nasal cannula (HFNC) or non-invasive mechanical ventilation (NIMV). Use of IMV, HFNC, or NIMV for ventilatory support during a procedure, or use of NIMV for the treatment of obstructive sleep apnea, will not be considered as meeting the definition of severe respiratory failure. Severe renal failure will be defined as the initiation of renal replacement therapy. Severe cardiovascular failure will be defined as the use of vasopressor or inotropic support for ≥48 hours. Use of vasopressor or inotropic support during a procedure will not be considered as meeting the definition of severe cardiovascular failure.

The proportion and 95% CI of patients who developed severe respiratory failure or severe renal failure or severe cardiovascular failure will be displayed and analyzed in the same way as the rehospitalization for acute pancreatitis through Day 30. The proportion of and 95% CI of patients who developed more than one organ failure (multi-organ failure) will be also displayed and analyzed. The mean duration of severe respiratory failure, severe renal failure, and severe cardiac failure will be summarized by treatment groups.

Given the previous results from study CM4620-204, a sensitivity analysis that will combine the subjects from the 1.25 mL/kg and 0.625 mL/kg groups into one combined group and will combine the subjects from the 0.3125 mL/kg and placebo groups into another combined group. The proportion and 95% CI of patients who developed severe respiratory failure, as well as those who developed multiorgan failure, in the two combined groups will be displayed and analyzed in the same way as the re-hospitalization for acute pancreatitis through Day 30.

A gMCP-Mod analysis of severe respiratory failure will be conducted in the same three steps method as Session 8.6.1.

• Step 1: Conventional Step – Odds Ratio Between Each Dose Versus Placebo

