The rate of severe respiratory failure will be analyzed using the logistic regression with treatment, sex (male or female) and the risk for organ failure (higher or lower) as covariates to obtain treatment effects and corresponding variance covariance matrix.

• Step 2: Candidate Models and Multiple Testing Procedure

Protocol CM4620-203 CONFIDENTIAL Page 22 of 31

The optimal contrast based on Candidate models for Auxora dose for the logit of rate of severe respiratory failure follows the following table

Model	Contrast coefficients for dose						
	Placebo	0.5 mg/kg	1.0 mg/kg	2.0 mg/kg			
Emax	0.866	-0.264	-0.293	-0.308			
sigEmax	0.663	0.300	-0.424	-0.539			

Note: Candidate model of Emax model is based on the assumption of parameter of ED50=0.026 mg/kg. Candidate model of sigEmax mode is based on the assumption of parameters of ED50=0.606 mg/kg and h=4.3

• Step 3: Dose-finding step – Dose-Response Model Fitting

The procedure is the same as the step 3 of Session 8.6.1.

The proportion and 95% CI of patients who developed new onset persistent respiratory failure or new onset persistent renal failure or new onset persistent cardiovascular failure will be displayed and analyzed in the same way as rehospitalization for acute pancreatitis through Day 30. New onset is defined as organ failure that was not present at randomization. Persistent is defined as ≥48 hours. Respiratory failure, renal failure, and cardiovascular failure are defined by a score of ≥2 on the modified Marshall scoring system. Patients with a known medical history of chronic kidney disease will be excluded from the analysis of new onset renal failure.

8.7.9 Mortality by Day 30

Mortality is recorded at the Day 30 follow-up assessment. The proportion and 95% CI of patients who died by Day 30 will be displayed and analysed in the same way as the re-hospitalization for acute pancreatitis through Day 30. If the Day 30 vital status is unknown and the patient has been discharged, the patient will be treated as alive.

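### SAP 8.7.8 defines new-onset persistent organ failure by Marshall score ≥2 alone, dropping protocol Appendix 1's organ-support, creatinine-rise and CKD criteria without declaring it

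*SAP*

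**What the plan says.** SAP 8.7.8 contains two organ-failure analyses.

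- **Severe failure** comes first, and the section ties incidence, severity and duration to it. It is based on support: any invasive ventilation, or at least 48 h of high-flow nasal cannula (HFNC) or non-invasive ventilation (NIMV); any start of renal replacement therapy (RRT); and for the circulation, "Severe cardiovascular failure will be defined as the use of vasopressor or inotropic support for ≥48 hours". Support during a procedure, and NIMV for sleep apnea, do not count.
- **New-onset persistent failure** comes at the end of the section. "New onset is defined as organ failure that was not present at randomization" and "Persistent is defined as ≥48 hours". The organ definition is "Respiratory failure, renal failure, and cardiovascular failure are defined by a score of ≥2 on the modified Marshall scoring system". For the renal part, "Patients with a known medical history of chronic kidney disease will be excluded from the analysis of new onset renal failure".

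Protocol Appendix 1 defines failure of each organ by alternatives. A physiological limit is enough, and so is support. The cardiovascular alternative is "The use of either vasopressor or inotropic support", the renal one is "The initiation of renal replacement therapy", and the respiratory one is HFNC, NIMV or invasive ventilation. Appendix 1 adds a creatinine rise of at least 300% when a pre-admission value is known. For CKD it replaces the 1.9 mg/dL limit with a level above 4.0 mg/dL.

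The Marshall table, printed in the same appendix, scores only PaO2/FiO2, creatinine and systolic pressure (with fluid response and pH). Its cardiovascular row is labelled "CV no inotrope". SAP Section 13 lists one change from the protocol, about ICU length of stay.

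**The concern.** Organ support acts on the variables that the Marshall table scores. If support is not itself a criterion, effective support can end or prevent a scored spell of failure while the patient still depends on it. The patients lost are therefore a selected group: those in whom support worked.

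Persistence of 48 h or more is the protocol's own concept (Section 1.1). This is the only SAP analysis that combines it with a physiological definition of failure. It is compared with placebo arm by arm under a named secondary endpoint, so its label should mean what the protocol means by organ failure.

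**Working it through.** The plan states no figure on this point, so there is none to reproduce. The check sets the definitions side by side and applies them to example patients.

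**Where the definitions agree.** Appendix 1's absolute limits without CKD (PaO2/FiO2 ≤300, creatinine ≥1.9 mg/dL, systolic pressure (SBP) <90 mmHg not fluid responsive) are the cut-offs for a Marshall score of 2. The difference lies only in the support criteria, the 300% rise and CKD.

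**Example patients.** These are illustrations, not data. Values not mentioned are normal, and there was no earlier 48 h spell with a score ≥2.

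| Case | Appendix 1 | Persistent (Marshall ≥2 for ≥48 h) | Severe |
|---|---|---|---|
| 1. Vasopressor 72 h, SBP 95 | Failure, 72 h | No: ≥2 not reached | Yes: 72 ≥ 48 |
| 2. RRT 72 h, creatinine 1.5 | Failure | No: score 1 | Yes: RRT started |
| 3. HFNC 72 h, PaO2/FiO2 320 | Failure, 72 h | No: score 1 | Yes: 72 ≥ 48 |
| 4. SBP <90 not fluid responsive 20 h, then vasopressor 30 h with SBP ≥90 | 20 + 30 = 50 h | No: 20 < 48 | No: 30 < 48 |
| 5. PaO2/FiO2 ≤300 for 24 h, then HFNC 30 h at 320 | 24 + 30 = 54 h | No: 24 < 48 | No: 30 < 48 |
| 6. CKD, creatinine rises above 4.0 for ≥48 h, no RRT | Failure | Excluded | No |
| 7. No CKD, creatinine 0.4 to 1.6 for ≥48 h | (1.6 − 0.4)/0.4 = 300%: failure | No: score 1 | No |
| 8. No CKD, creatinine 2.2 for 72 h, no RRT | Failure | Yes: score 2 | No |

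Cases 1 to 3 drop out of the persistent analysis but are caught as severe. Cases 4 to 7 are missed by both. Case 8 shows that without support the Marshall rule and Appendix 1 agree, and that the persistent analysis adds patients whom the severe analysis does not count.

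**How wide each gap is.**

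- *Cardiovascular.* The row label leaves a patient on an inotrope without a score and says nothing about vasopressors. SBP ≥90 reads as 0 or as unscored; neither reaches 2. The analysis is to follow the method of SAP 8.7.4, which imputes unknown status as no. If that rule carries over, unscored patients become non-events.
- *Renal.* A dialysed patient is missed only if creatinine was not at 1.9 or more for 48 h. A fall from 5.2 to 1.7 mg/dL takes the score from 4 to 1; what counts is how long it stayed at 2 or above.
- *300% rise.* Without CKD this adds patients only while creatinine stays below 1.9, so the pre-admission value must be below 1.9/4 = 0.475 mg/dL. Section 8.12.1 collects that value only if available. This gap is narrow.
- *Respiratory.* In Appendix 5, supplemental oxygen gives an imputed ratio above 300 only at FiO2 0.24 with SpO2 0.95 or 0.96 (315, 341) or FiO2 0.27 with SpO2 0.96 (303). At FiO2 0.30 or more no entry exceeds 273, and the table stops at SpO2 0.96. The gap therefore needs a blood gas, a low FiO2 or a saturation beyond the table.

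**Sampling.** Vital signs and SpO2/FiO2 are scheduled once daily to 240 h. Post-baseline chemistries are at 24, 48, 72, 120, 168 and 216 h and Day 30. The Day 12 to 28 visits schedule none of these. A single reading normalised by support can therefore break a 48 h spell.

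**The case against.** The strongest reply is that the first analysis in 8.7.8 is support-based. Any start of RRT, and any vasopressor or inotrope use of 48 h or more outside a procedure, counts there. This stands. A reader might infer that a patient on a vasopressor or on dialysis is recorded in this trial as free of organ failure. The documents do not support that: the loss is confined to one secondary proportion, plus the patients in cases 4 to 7.

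It can also be said that one analysis measures support and the other physiology, so a patient who meets only one is no contradiction. That stands too. The objection is to the undeclared gap from Appendix 1, not to having two measures.

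The Marshall table is part of Appendix 1, and protocol 10.7 leaves the details of other secondary endpoints to the SAP. The sponsor may therefore choose this scale. But the operative definitions in Appendix 1 include the support alternatives, and a narrower rule should be declared.

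A reader might also say that the table gives score 0 to a supported patient with SBP ≥90. For a patient on an inotrope it gives no score, so part of the fault is a missing rule.

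Lastly, excluding CKD is coherent on an absolute creatinine scale, where a raised baseline could pass for failure. That justifies not applying Marshall to these patients. It does not justify leaving aside the CKD criteria that the protocol provides.

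**Conclusion.** The point holds in limited form. SAP 8.7.8's new-onset persistent analysis uses a narrower definition of organ failure than protocol Appendix 1, and Section 13 does not say so. As written, patients whose scored variable is normalised by support can be counted as non-events in it. Many are still captured as severe failure. Two groups are clearly missed by both analyses: those whose physiological failure and support together last 48 h or more while the support itself lasts less than 48 h (invasive ventilation and RRT aside), and CKD patients with creatinine above 4.0 mg/dL and no RRT. The 300% rise adds few.

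The number affected cannot be derived, because the documents give no rates of vasopressor, ventilatory or renal support. The conclusion rests on reading the Marshall rule literally, as the sole criterion, for lack of any other rule in 8.7.8. It touches no sample size, alpha or primary result. It is worth correcting before database lock because the correction is cheap.

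**What to change.** In the new-onset persistent paragraph of SAP 8.7.8:

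1. Define respiratory, renal and cardiovascular failure as in protocol Appendix 1: the physiological limit or the listed organ support. Apply the same rule at randomization when deciding what is new.
2. Carry over all of 8.7.8's exclusions: ventilatory or vasopressor/inotropic support during a procedure, and NIMV for obstructive sleep apnea. Without the second, nightly sleep-apnea treatment could count as respiratory failure.
3. Count persistence over continuous time meeting either criterion. Treat RRT as met from initiation until RRT ends, because initiation alone has no duration.
4. Classify CKD patients by Appendix 1's CKD criteria instead of excluding them, using the relative rise only where a pre-admission creatinine exists.
5. Keep the Marshall-only version as a sensitivity analysis if wanted, with a stated rule for patients on support.
6. List any remaining departure from Appendix 1 in Section 13.

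The cost is one paragraph and a small programming change. The severe analysis already needs the support data, including durations. Event counts will probably be slightly higher.

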8.7.10 Change in Pain Score

Pain numeric rating scales are recorded through the Day 10 visit and at the Day 30 visit. The mean score at each visit and mean changes from baseline to each post-baseline visit of the pain numeric rating scale will be summarized by the treatment group.

8.8 Exploratory Endpoints

The development of infected pancreatic necrosis, and of sepsis will be summarized by the number of patients and treatment group.

Protocol CM4620-203 CONFIDENTIAL Page 23 of 31

Mean changes in total mGCSI-DD score from screening to discharge and to Day 30, IL-6 levels, and urine neutrophil gelatinase-associated lipocalin (NGAL) levels to each post-baseline visit will be summarized by the treatment groups.

The mean change in IL-6 levels in patients with a baseline level ≥150 pg/mL to the 72-hour visit will be summarized by the treatment group. The change in urine NGAL in patients with a baseline level ≥150 ng/mL to the 72-hour visit will be summarized by the treatment groups.

Shift tables will display the number of patients with baseline IL-6 levels >1000 pg/mL, 150-1000 pg/mL at 72 hours by the treatment groups.

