Patients will complete the modified American Neurogastroenterology and Motility Society (ANMS) Gastrointestinal Cardinal Symptom Index Daily Diary (mGCSI-DD) worksheet at the baseline assessment, at 96 hours, 168 hours, Day 14 and Day 21 (for patients who remain hospitalized on these days), on the day of discharge, and daily at bedtime after discharge until the Day 30 visit. Patients who are discharged on Days 25-29 will not complete the mGCSI worksheet after discharge.

It is recommended that all patients randomized in the study should receive care consistent with the 2018 American Gastroenterological Association (AGA) Institute Technical Review of the Initial Medical Management of Acute Pancreatitis. Patients should receive local SOC for the management of other medical conditions.

In patients with AP, the AGA strongly recommends early oral feeding (within 24 hours) rather than keeping the patient nil per mouth (Nil per Os, NPO). Patients randomized into the study, therefore, will be offered a low fat, ≥500-calorie solid meal at each mealtime after the infusion of the first dose of study drug if alert and not on mechanical ventilation, or if not NPO for a planned surgery/medical procedure, or if not NPO because of an acute medical condition. If the patient does not wish to eat the solid meal when offered or is unable to tolerate the solid meal, they should then be offered a liquid meal. The same approach should occur at each subsequent mealtime until discharge. When patients eat a solid meal, it should be recorded if they ate ≥50% of the meal and

if they either vomited or experienced an increase in abdominal pain in the two hours after the meal.

It is also recommended that all patients randomized in the study should not be discharged from the hospital until solid food is tolerated, abdominal pain has resolved or been adequately controlled, and there is no clinical evidence of infection necessitating continued hospitalization. Tolerating solid food is defined as eating ≥50% of a low fat, ≥500-calorie solid meal without an increase in abdominal pain or vomiting. If the patient is not tolerating either solid or liquid meals, tube feedings should be considered.

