5.3 Discharge Criteria

The patient randomized to receive study drug should remain in the hospital until all 3 doses of study drug have been administered. The criteria for medically indicated discharge from the hospital are:

- Abdominal pain has resolved or is controlled with medications;
- Solid food is tolerated, which is defined as eating ≥50% of a low fat, ≥500 calorie solid meal without an increase in abdominal pain or vomiting;

• There is no clinical evidence of an infection necessitating continued hospitalization.

In the scenario where the PI or treating physician wants the infusion(s) to begin earlier than the 24 hour +/- 1 hour window (e.g. the patient is ready to be discharged before all 3 doses of study drug have been administered and / or to facilitate an infusion time where study personnel are available), the PI or treating physician should contact the medical monitor to discuss whether it is appropriate to begin infusion earlier (up to 6 hours earlier) than the 24 hour +/- 1 hour protocol window.

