Patients will complete the modified American Neurogastroenterology and Motility Society Gastrointestinal Cardinal Symptom Index Daily Diary (mGCSI-DD) worksheet at the baseline assessment, at 96 hours, 168 hours, Day 14 and Day 21 (for patients who remain hospitalized on these days), on the day of discharge, and daily at bedtime after discharge until the Day 30 visit. Patients who are discharged on Days 25-29 will not complete the mGCSI worksheet after discharge.

It is recommended that all patients randomized in the study should receive care consistent with the 2018 American Gastroenterological Association (AGA) Institute Technical Review of the Initial Medical Management of Acute Pancreatitis. Patients should receive local standard of care (SOC) for the management of other medical conditions.

In patients with acute pancreatitis, the AGA strongly recommends early oral feeding (within 24 hours) rather than keeping the patient nil per mouth (Nil per Os, NPO). Patients randomized into the study, therefore, will be offered a low fat, ≥500-calorie solid meal at each mealtime after the infusion of the first dose of study drug if alert and not on mechanical ventilation. If the patient does not wish to eat the solid meal when offered or is unable to tolerate the solid meal, they should then be offered a liquid meal. The same approach should occur at each subsequent mealtime. When patients eat a solid meal, it should be recorded if they ate ≥50% of the meal and

Protocol CM4620-203 CONFIDENTIAL Page 7 of 31

if they either vomited or experienced an increase in abdominal pain in the two hours after eating a meal.

It is also recommended that all patients randomized in the study should not be discharged from the hospital until solid food is tolerated, abdominal pain has resolved or been adequately controlled, and there is no clinical evidence of infection. Tolerating solid food is defined as eating ≥50% of a low fat, ≥500-calorie solid meal without an increase in abdominal pain or vomiting. If the patient is not tolerating either solid or liquid meals, tube feedings should be considered.

All protocol required laboratory testing, except biomarker and PK samples, will be performed at the local laboratory. Results from the biomarkers and PK blood samples collected as part of the protocol and being tested at a central lab will not be available to assist the PI or treating physician in managing the patient.

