8.6.3 Main Analytical Approach

Time to solid food tolerance through Day 30 visit will be analyzed based on the Generalized Multiple Comparison Modelling (gMCP-Mod) approach described in Session 8.6.1.

Time to solid food tolerance is defined as the number of hours from the date and time of the SFISD for the patient to the first date and time the patient receives a solid meal that is tolerated. If the mealtime was not recorded, the mealtime will be estimated using the middle time of the meal serving interval.

Tolerating a solid meal is defined as eating \geq 50% of a low fat, \geq 500-calorie solid meal without an increase in abdominal pain or vomiting within the two hours of mealtime. In addition, to meet the definition, all subsequent meals during the hospitalization should not show an increase in abdominal pain or vomiting within the two hours of mealtime. If a procedure that could impact food tolerance is performed after a solid meal is initially tolerated that results in subsequent meals not being tolerated, the time of the initial tolerated meal will be considered in the calculation of the time to solid food tolerance. The procedures that impact food tolerance and/or its assessment are defined as (1) a procedure that requires a period of nil by mouth (2) a procedure and/or treatment that causes gastrointestinal dysfunction e.g., cholecystectomy, necrosectomy. The procedures performed after the initial food tolerance will be reviewed before the database lock to identify the procedures that could impact the time to the tolerated solid food. If the subject was not discharged from the hospital during the study and did not tolerate solid food, the time to solid food tolerance will be censored at the latest date and time of the hospital stay.

If a patient is discharged home without tolerating solid food, the daily record of the modified American Neurogastroenterology and Motility Society Gastrointestinal Cardinal Symptom Index Daily Diary (mGCSI-DD) at or after hospital discharge will be used in the calculation of the time to solid food tolerance. The patients who did not tolerate solid food while hospitalized will be considered as tolerating solid food at or after hospital discharge at 8am on the first of three consecutive days where the following 4 criteria are met for the mGCSI-DD:

Protocol CM4620-203 CONFIDENTIAL Page 17 of 31

- none for vomiting
- none or mild for nausea

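### The symptom diary is summarised only at discharge and Day 30, so it can mask or shrink a benefit of faster recovery that scores already collected at common times could show

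*SAP*

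**What the plan says.** SAP 8.8 gives the planned diary analysis as "Mean changes in total mGCSI-DD score from screening to discharge and to Day 30", by treatment group. The sentence goes on to IL-6 and urine NGAL, and for these it refers to "levels to each post-baseline visit will be summarized by the treatment groups". As the sentence is built, that phrase attaches to the biomarkers and not clearly to the diary. SAP 8.7.10 summarises the pain score at each post-baseline visit.

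The diary is collected more often than SAP 8.8 uses it. SAP 3.1 schedules it "at the baseline assessment, at 96 hours, 168 hours, Day 14 and Day 21 (for patients who remain hospitalized on these days"), and Protocol 3.1 lists the same times. It is also completed on the day of discharge and then every evening at home until the Day 30 visit. The one exception is patients discharged on Days 25-29, who stop at discharge.

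On discharge, Protocol 3.1 recommends that patients "should not be discharged from the hospital until solid food is tolerated, abdominal pain has resolved or been adequately controlled", and that no infection needs further hospital care. Protocol 5.3 words the pain criterion as "Abdominal pain has resolved or is controlled with medications" and adds that a patient "should remain in the hospital until all 3 doses of study drug have been administered". Protocol 8.12.10 describes the use of the diary as exploratory.

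**The concern.** The diary (Protocol Appendix 6) asks about nausea, unfinished meals, fullness, abdominal pain, vomiting and overall severity. Three of these overlap with the discharge criteria: pain, vomiting, and eating. The SAP itself treats diary items as a marker of recovery. Under SAP 8.6.3, three consecutive days with no vomiting and at most mild nausea, unfinished meals and pain count as solid food tolerance in a patient sent home without it. SAP 8.7.2 uses the same rule for medically indicated discharge.

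Reading the diary on the day of discharge therefore comes close to reading it at the moment of the outcome. If one dose shortens recovery, its patients are scored earlier but in much the same state as placebo patients who are scored later. Scores at common times would separate the groups, and SAP 8.8 does not name them for this endpoint.

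The stake is limited but real. Protocol 1.6 says that the study should inform the choice of Phase 3 endpoints. A summary that is insensitive to speed of recovery could lead the sponsor to set aside a useful multi-symptom measure.

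**Working it through.** The documents give no effect size, standard deviation, test or power for the diary, so there is no planned figure to reproduce. The check has three parts.

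**1. When recovery happens, on the documents' own figures.** Protocol 1.5.2 reports a phase 2a median stay of 3.70 days (3.70 × 24 = 88.8 h) on Auxora and 6.02 days (144.5 h) on supportive care alone. Median time to solid food was 57 h (low dose), 78.5 h (high dose) and 100 h (supportive care). That study was small (14 and 7 patients) and open-label. It still suggests that discharge time can differ by group and that Day 30 (720 h) comes long after typical recovery.

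**2. Proportion not yet recovered at each time.** Inputs: the planning medians for tolerating solid food in SAP 4, 144 h and 72 h. Assumption: exponential times, so the proportion not recovered at time t is 2^(−t/median).

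| Time | Median 144 h | Median 72 h |
|---|---|---|
| 96 h | 2^(−96/144) = 0.630 | 2^(−96/72) = 0.397 |
| 168 h | 0.445 | 0.198 |
| Day 14 (336 h) | 0.198 | 0.039 |
| Day 30 (720 h) | 0.031 | 0.001 |

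The groups are far apart at 96 h and 168 h and almost together at Day 30.

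**3. What this does to a score (illustration only).** A simulation of 400,000 patients per group used these recovery times and an assumed score model:
- total score 0-16, baseline mean 10 (SD 3);
- linear fall to a residual of 2 (SD 1.5) at recovery, then a half-life of 5 days;
- discharge at the later of recovery and 52 h (48 h to the third infusion plus 4 h to give it);
- 0% to 30% of patients marked for possible early discharge, at a random time between 52 h and 168 h if not yet recovered.

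| Score read at | Active minus placebo, mean change | Approximate power, 54 per group, two-sided 0.05 |
|---|---|---|
| Discharge | −0.06 (no early discharge) to −0.47 (30%) | 3% to 11% |
| 96 h | −1.59 | 64% |
| 168 h | about −1.35 | 53% |
| Day 14 | about −0.79 | 25% |
| Day 30 | about −0.2 | 5% |

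Power here counts only the tail in the direction of the effect, so no effect at all would give 2.5%. No test of the diary is planned. The power column only shows how much signal each reading time carries under this model.

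**Can the data support common times?** At 96 h, 168 h, Day 14 and Day 21 an inpatient has a worksheet scheduled, a patient leaving that day has the discharge-day score, and a discharged patient has that evening's diary. The Days 25-29 exception does not affect any of the four times, because those patients are still in hospital on Day 21. A score is therefore scheduled for every survivor at each time.

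**The case against.** The strongest reply has four parts.

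*Discharge is not the only reading.* Day 30 is in the same sentence and is a common time. This is correct, and a reader who took the diary to be analysed at discharge alone would be wrong. Day 30 does little for speed of recovery, but that judgement rests on assumed or phase 2a recovery times.

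*Discharge is not defined by the diary.* The criteria are a recommendation, and pain need only be controlled. Half of one meal is enough, nausea and fullness are not criteria, and the diary records the worst of the past 24 hours. The three infusions also set the length of stay. SAP 8.6.3 foresees patients who leave unrecovered: "If a patient is discharged home without tolerating solid food, the daily record of the modified" diary is then used for the primary endpoint. All of this stands. It is why a reader should not infer that the change to discharge must show no benefit. A model in which everyone leaves at the same fixed fraction of baseline gives a difference of exactly zero, but only because the zero was assumed.

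*Speed of recovery is measured elsewhere.* Time to solid food tolerance, time to medically indicated discharge and the pain score at each visit all address it. This also stands, and it rules out any reading that the trial cannot show faster relief.

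*The phrase on post-baseline visits may cover the diary too.* This would not settle the matter. SAP 8.1.6 bases analysis on eCRF visits, and the scheduled worksheets at 96 h and 168 h come only from patients still in hospital. Unless home diaries are merged in, that comparison would keep the slow recoverers of each group.

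**Conclusion.** The point holds as a minor one. The change to discharge is read at a time that depends on the outcome, and can mask or shrink a benefit of faster recovery. Day 30 is probably too late to make up for it. Scores at common times between these two are collected but not named for this endpoint.

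The size cannot be taken from the documents. In the illustration the difference at discharge is 4% to 30% of the difference at 96 h (0.06/1.59 and 0.47/1.59). It rests on exponential recovery at the planning medians and on a score model that has no source in the documents. The direction follows from the design of the analysis; the numbers do not.

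The trial's efficacy conclusions and its primary dose-response analysis are untouched. What suffers is the use of the diary in choosing Phase 3 endpoints.

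**What to change.** In SAP 8.8, add descriptive summaries by treatment group of change in mGCSI-DD score at 96 h, 168 h, Day 14 and Day 21 from SFISD. State that the hospital worksheet is used for inpatients and the same day's home diary for discharged patients, so that the comparison is not limited to those still in hospital. Keep discharge and Day 30 as descriptive summaries. A mixed model adjusted for baseline score is optional.

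Settle three details in the same edit:
- Name the baseline assessment as the reference, not screening. Protocol 8.2 and the schedule of events place the first diary there. This does not change any number, because only one pre-dose diary is scheduled.
- Give a simple rule for deaths and for missing diaries, and report how many scores are available by group at each time.
- Define the total score. The SAP does not, and the diary mixes severity boxes with a count of vomiting episodes.

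The cost is SAP text and one derived dataset that joins the two diary sources. No new data are collected. The downside is that some home diaries will be missing, possibly to a different extent in each group.
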